9.2.1 Definition of Treatment Emergent Adverse Event (TEAE)

TEAE means any untoward medical occurrence associated with the use of an intervention in humans, whether or not considered intervention-related (21 CFR 312.32 (a)). An TEAE can therefore be any unfavorable and unintended sign (including an abnormal clinical laboratory finding), symptom or disease temporally associated with the use of medicinal (investigational) product.

COVID-19 is a progressive disease and any worsening or new signs and symptoms consistent with mild to moderate COVID-19 disease during the first 3 days will not be recorded as TEAEs. Worsening of disease will be recorded as a clinical outcome measure as outlined in Section 6.4. Any worsening of the eight individual COVID-19 signs and symptoms from baseline (moderate or greater) or new signs and symptoms that first occur on or after study day 4 (moderate or greater), as reported on participant self-assessment daily diary cards or during clinic visits, will be recorded as a TEAE with attribution to COVID-19 disease pathogenesis or the investigational device at the discretion of site investigators. Any COVID-19 related TEAEs will be assessed daily and considered resolved when the symptom is none (0) or mild (1) on the Diary Card.

Any medical condition that is present at the time that the subject is screened will be considered as baseline and not reported as an TEAE. However, if the severity of any pre-existing medical condition increases, it should be recorded as an TEAE.

TEAEs can be further divided into solicited TEAEs and unsolicited TEAEs. Solicited TEAEs are those for which the study team will specifically query the subject whether they occurred. Unsolicited TEAEs are those events that the subject report occurring without being queried about the specific event.

All TEAEs will be assessed for severity and relationship to study intervention. Reporting of all TEAEs, solicited and unsolicited, will occur during the period from study device administration on Day 1 through Day 14 or until an early termination visit.

All TEAEs, solicited and unsolicited, will be captured on the appropriate source documents and e-CRFs. Information to be collected for TEAEs includes event description, date of onset, assessment of severity, relationship to study product and alternate etiology (assessed only by those with the training and authority to make a diagnosis as the participating clinical site PI or appropriate sub-investigator), date of resolution, seriousness, and outcome. All TEAEs will be documented regardless of relationship.

TEAEs will be followed to resolution or stabilization.

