4.1.2 Study Design

Subjects will provide written informed consent prior to initiating any screening procedures. Subjects meeting all screening criteria will be eligible for enrollment and randomization into the study. Subjects with COVID-19 disease with signs and symptoms reported > 72 hours from onset will be given instructions to see their primary care physician or be advised to seek potential treatment (if eligible) at a local antibody infusion center.

This Phase II, dose finding portion of the trial is targeting to enroll a minimum of 60 volunteers with 30 in each of at least two dosing cohorts (20 assigned to RD-X19 and 10 assigned to sham per cohort, 2:1 randomization).

Cohort A will begin with 24 J/cm² per treatment, administered 2X/Day for duration of 7 days. Once 80% of subjects (n=24) in Cohort A complete the Day 8 visit and no predefined safety signals as outlined in the study pausing/stopping criteria have been observed, Cohort B, 32 J/cm² per treatment will start enrollment. In the event device-related serious adverse events or patterns of device-related adverse events, including application site reactions, are observed in Cohort A, and based on the review and recommendation of the external safety monitoring committee (SMC) of unblinded data, the study may proceed with enrollment and dosing in Cohort C, 16 J/cm² per treatment in keeping with SMC recommendations. An illustration of the ascending (or descending) dose finding design is provided below.

Cohort A: RD-X19 24 J/cm² vs. Sham

[figure not shown]
(5 minute treatment, 2X/Day for a duration of 7 days)

Cohort B: RD-X19 32 J/cm² vs. Sham

(5 minute treatment, 2X/Day for a duration of 7 days)

Cohort C: RD-X19 16 J/cm² vs. Sham

(5 minute treatment, 2X/Day for a duration of 7 days)

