5.2 Risk/Benefit Assessment

5.2.1 Known Potential Risks

The potential risks of participating in this trial are those associated with having blood drawn and mild, transient, local reactions as measured in EB-P10-01, a Phase I Open Label, Acute Safety Study of the EmitBio RD-X19 Device in healthy adults. There were no SAEs, TEAEs (including local reactions) attributed in EB-P12-01, a Phase I/II randomized, sham controlled, double-blinded trial in indivuals with mild to moderate COVID-19. See the Clinical Investigators Brochure for more detail.

Drawing blood may cause transient discomfort and fainting. Fainting is usually transient and managed by having the subject lie down and elevate his/her legs. Bruising at the blood draw site may occur but can be prevented or lessened by applying pressure to the blood draw site for a few minutes after the blood is taken.

Extensive evaluation of the RD-X19 and similar energy-based devices routinely used for oral and skin care purposes resulted in the Sponsor, after careful consideration, making the determination that RD-X19 ia a “Not Significant Risk” (NSR) device per FDA guidelines. This was affirmed twice by protocol Institutional Review Boards (IRBs).

CAUTION - The light emitted may be harmful to the eyes. Do not stare at the light. Photobiological eye safety testing has classified this device as Risk Group 2 - Moderate risk. The blue light emitted does not pose an immediate hazard due to aversion response to very bright light sources or due to thermal discomfort of prolonged exposures. However, direct illumination of unprotected eyes should be avoided. Study staff must ensure volunteers understand to never point the RD-X19 device toward their or anyone else's eyes.

A summary of the known and potential risks of the RD-X19 are as follows:

- Depth of insertion beyond recommended depth has the potential to result in pharyngeal gag reflex for some study subjects.

- Exposure to blue light may be harmful to the eyes when the device is used incorrectly.
- Overexposure of tissues to blue light can cause mild, transient pharyngeal discomfort and erythema.
- Extended blue light exposure to eyes may result in worsened headache pain associated with chronic migraines and other cerebral vascular disorders associated with headache.
- Shining the end of the RD-X19 illumination device directly onto skin, approximately 1 cm away has the potential to induce mild erythema.

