10.4.2 Safety Analyses

Summaries will be presented by treatment arm on the Safety Population. Adverse device effects will be coded using the latest version of the Medical Dictionary for Regulatory Activities (MedDRA). Treatment Emergent Adverse Events (TEAE), vital signs, and methemoglobin will be summarized using descriptive statistics. Other safety data including prior and concomitant medications will be listed.

TEAEs are any event not present prior to the initiation of the treatments or any event already present that worsens in either intensity following exposure to the treatments. Number and percent of subjects reporting TEAEs will be tabulated by treatment group. Summaries will be presented by system organ class and preferred term, and further by severity and relationship to study treatment. In the summaries of incidence rates (frequencies and percentages), severity and relationship to treatment, subjects who report more than one event that are mapped to the same preferred term will be counted only once under the strongest severity and relationship, accordingly.

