### 5.6.1 Adverse Events

All adverse events (AEs) occurring during the study will be recorded and coded in the Medical Dictionary for Regulatory Activities (MedDRA), version 24.0. TEAEs are defined as AEs recorded during or at any point after the first application of the study treatment. Exacerbations or worsening of any conditions during the trial that were present at screening and documented as part of medical history will also be recorded as TEAEs.

Frequency and percent of subjects reporting TEAEs will be tabulated for each treatment by system organ class (SOC) and preferred terms (PT) for the following:

- all TEAEs
- all TEAEs by severity
- all TEAEs by relationship to study treatment

In the summaries of incidence (frequencies and percentages) of all TEAEs, whether solicited or unsolicited, subjects who report more than one event that are mapped to the same PT will be counted only once. In the summaries of incidence of TEAEs by severity and by relationship to study treatment, subjects who report more than one event that are mapped to the same PT will be counted only once under the strongest severity and strongest relationship, accordingly. Incidence of TEAEs will also be tabulated by SOC and PT and further by what study day the ‘most severe’ observation was made.

Treatment-Emergent Serious Adverse Events (TESAEs) will be discussed within the clinical study report. TEAEs, TESAEs and TEAEs that led to treatment interruption or discontinuation will be presented in a tabular listing with attribution (device related, non-device related).

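### On Days 1–3 (6 of 14 doses), symptoms consistent with mild-to-moderate COVID-19 are not recorded as TEAEs, and no safety table by arm covers headache or sore throat in that window

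*Protocol*

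**What the plan says.** Protocol 9.2.1 gives COVID-19's progressive course as the reason for an exception: new or worse "symptoms consistent with mild to moderate COVID-19 disease during the first 3 days will not be recorded as TEAEs". It sends worsening of disease to the clinical outcome in Protocol 6.4. It then describes TEAE recording, with attribution to disease or device, for worsening of the eight symptoms and for "new signs and symptoms that first occur on or after study day 4 (moderate or greater" (the quotation stops before the closing bracket).

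Other sections define or report TEAEs without a 3-day gap:

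- Protocol 9.2.3 has unsolicited TEAEs of every severity reported for the whole study.
- Protocol 10.4.2: "TEAEs are any event not present prior to the initiation of the treatments", or that worsens after exposure.
- SAP 5.6.1: "TEAEs are defined as AEs recorded during or at any point after the first application of the study treatment".

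Protocol 5.2.1 lists two device risks that overlap with diary symptoms: "Overexposure of tissues to blue light can cause mild, transient pharyngeal discomfort and erythema" and "Extended blue light exposure to eyes may result in worsened headache pain associated with chronic migraines and other cerebral vascular disorders associated with headache". Sore throat and headache are two of the eight symptoms that subjects score twice daily.

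Protocol 9.2.2 solicits illumination-site pain, erythema and edema/induration, and any other oral mucosal pain or lesion, throughout the study. Headache is not on that list. SAP Tables 14.3.2 and 14.3.3 summarise reactogenicity and oropharyngeal findings by visit, including Day 1 and Day 3.

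**The concern.** The exception works before attribution. A headache or sore throat that starts after the first illumination, and that could be either disease or device, is left out because it resembles the disease. Nobody is asked which it was. The sham arm exists to answer that question by comparison, but no safety table in SAP 7.2 uses the Day 1–3 symptom scores.

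Two uses of the data are affected. One is the TEAE tables. The other is the pausing rule in Protocol 8.5.1 (three or more subjects with a related grade 2 or higher TEAE in one SOC grouping) and the stopping rule in Protocol 8.5.2. Both count TEAEs, and the step from Cohort A to Cohort B depends on them. Protocol 6.5.1 puts the starting energy per dose 50% above the previous study, with Cohort B up to 100% above it.

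**Working it through.** **1. Doses in the window.** The schedule is "5 minute treatment, 2X/Day for a duration of 7 days" (Protocol 4.1.2).

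- Total: 2 × 7 = 14. Days 1–3: 2 × 3 = 6. Both match the 6 and 14 in the per-protocol definition (Protocol 10.3). Its 75% threshold also reproduces: 0.75 × 14 = 10.5, rounded up to 11.
- Share on Days 1–3: 6/14 = 42.9%.

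**2. What the substitute outcome covers.** Protocol 6.4 counts worsening when the composite score exceeds baseline on or after Day 3.

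- Worsening confined to Days 1–2 is not counted: 2 × 2 = 4 doses, 4/14 = 28.6%.
- From Day 3, a one-grade rise in one symptom moves the average by 1/8 = 0.125. A one-grade fall in another symptom cancels it, so a new headache can be hidden by an improving cough.
- The outcome is reported as an efficacy endpoint (SAP Table 14.2.2.3), without attribution or a breakdown by symptom.

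**3. Routes for a Day 1–3 event.**

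| Event | TEAE route | Safety table by arm |
|---|---|---|
| Oral or illumination-site pain, erythema, edema | Yes, solicited (Protocol 9.2.2) | Yes (SAP Tables 14.3.2, 14.3.3) |
| Sore throat judged consistent with COVID-19 | No; no rule separates it from site pain | None |
| Headache without a prior headache disorder | No | None |
| Worsening of a pre-existing headache disorder | Pre-existing-condition rule in Protocol 9.2.1; precedence over the exception not stated | TEAE tables, if recorded |

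The diary yields 8 symptoms × 2 ratings × 3 days = 48 ratings per subject in the window. They appear in Listing 16.2.6.1 but in no safety table.

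**4. Illustration for the pausing count.** The true event rate and the unrecorded share are not in the documents, so both are assumed. Take 20 active subjects in a dose-finding cohort (Protocol 4.1.2). Let *p* be the true rate of related grade 2 or higher events in one SOC, all of a kind that falls under the exception, and *h* the share unrecorded. Then q = p(1 − h), and P(at least 3 of 20) = 1 − Σ C(20,k) q^k (1 − q)^(20−k) for k = 0 to 2.

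| p | h = 0 | h = 4/14 | h = 6/14 |
|---|---|---|---|
| 10% | 0.323 | 0.168 | 0.103 |
| 20% | 0.794 | 0.560 | 0.405 |
| 30% | 0.965 | 0.834 | 0.691 |

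In an expanded final cohort with 120 active subjects (20 + 100, SAP 3.3), the probability at p = 10% falls only from 1.000 to 0.970 with h = 6/14. The loss matters mainly in the small cohorts. Setting *h* equal to the dose share is a convenience, not an estimate.

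**The case against.** The strongest reply is that the throat risk in Protocol 5.2.1 is already captured. Site pain and erythema are solicited by direct questioning, subjects are observed for 30 minutes after the first illumination with an oropharyngeal examination, and both sets of findings are tabulated by dose and pooled sham for Day 1 and Day 3. This stands. A reader might infer that early device harm goes unrecorded altogether, or that the sham comparison is lost for the first three days. For local oral reactions the documents show the opposite.

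Other replies also carry weight:

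- The headache risk is narrow. It is tied to extended eye exposure and existing headache disorders, and a worsening pre-existing condition is to be recorded as a TEAE. Nausea is not a listed device risk.
- Nothing in the documents shows that reactions concentrate in the first exposures. The 6/14 is a share of doses, not of events.
- The Day 4 limit may apply only to new symptoms. On that reading, a symptom that worsens on Day 2 and is still worse on Day 4 would be recorded. The text allows either reading.
- SAP 5.6.1 depends on what is recorded, so it does not by itself contradict Protocol 9.2.1. Protocol 10.4.2 can be read as a general definition with 9.2.1 as a specific exception. Protocol 9.2.3 is harder to read that way.
- The exception has a rationale. In the earlier sham-controlled study all TEAEs were attributed to COVID-19 (Protocol 4.1), so recording every early symptom would add many disease events.

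One reply holds only in part: that severe events fall outside the exception. Protocol 6.1 keeps symptom scoring separate from the classification of disease severity at baseline, and Protocol 7 bases severe COVID-19 on clinical signs. A grade 3 headache in a subject without those signs could still be treated as consistent with mild-to-moderate disease.

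**Conclusion.** The point holds in a limited form. On Days 1–3, a headache, or a sore throat judged to be COVID-19, can miss both the TEAE tables and the TEAE-based pausing and stopping counts. If it is confined to Days 1–2, it also misses the worsening outcome. The window is 6 of 14 doses (43%), and the part with neither route is 4 of 14 (29%). The number of device-caused events lost cannot be derived from the documents, and the pausing-rule probabilities above rest on assumed rates.

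Whether every early COVID-like symptom should be a TEAE is a debatable trade between noise and sensitivity, and this point does not turn on it. What the plan lacks is a sham-controlled summary of scores it already collects, and consistent wording on when the exception applies. This is a cheap improvement, not a failure of the safety plan.

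**What to change.** 1. Add one descriptive table to SAP 5.6, with the columns already set there (each RD-X19 dose, pooled RD-X19, pooled sham). It would show the number and percentage of subjects with new or worsened grade 2 or higher sore throat, and likewise headache, on Days 1–3 after first treatment; all eight symptoms could optionally be shown. Count a score of 2 or 3 that exceeds the subject's baseline score for that symptom. Use observed diary entries and report how many are missing.
2. Reconcile Protocol 9.2.1, 9.2.3 and 10.4.2 and SAP 5.6.1 on whether the 3-day exception applies. State in 9.2.1 whether the Day 4 limit covers worsening symptoms as well as new ones.

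The cost is one table from existing data and a wording change. The table needs no new recording at sites, so it remains possible even though SAP 3.1 describes the enrolment increase in the past tense. The downside is that most events will be disease-related, so the table can be read only against sham.

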9.2.2 Solicited Treatment Emergent Adverse Events - Reactogenicity

Solicited TEAEs are anticipated TEAEs for which consistent collection of information is desired. Study clinicians will follow and collect resolution information for any reactogenicity symptoms that are not resolved during the active study period.

Solicited TEAEs (i.e., reactogenicity) will be collected by direct questioning of study subjects and recorded on the appropriate source document and e-CRF during the entire course of the study.

For this study, solicited AEs include:

- Illumination site Pain
- Illumination site Erythema
- Illumination site Edema/Induration
- Any other pain, redness, swelling or lesion of the oral mucosa

9.2.3 Unsolicited Treatment Emergent Adverse Events

All TEAEs spontaneously reported by the subject and/or in response to an open question from study staff or revealed by observation, physical examination or other diagnostic procedures must be recorded on the appropriate source document and e-CRF.

Unsolicited TEAEs of all severities will be reported during the entire course of the study.

9.2.4 Treatment Emergent Adverse Event Reporting

Information on all TEAEs should be recorded on the appropriate source document and e-CRF. All clearly related signs, symptoms and results of diagnostic procedures performed because of an TEAE should be grouped together and recorded as a single diagnosis. If the TEAE is a clinical laboratory abnormality that is part of a clinical condition or syndrome, it should be recorded as the syndrome or diagnosis and be described in terms of duration (start and stop date).

9.2.5 Definition of a Serious Adverse Event (SAE)

An SAE is defined in 21 CFR 312.32 as follows: “An AE is considered serious if, in the view of either the participating clinical site PI or appropriate sub-investigator or the sponsor, it results in any of the following outcomes:

- Death,
- A life-threatening AE,
- Inpatient hospitalization or prolongation of existing hospitalization,
- A persistent or significant incapacity or substantial disruption of the ability to conduct normal life functions,
- Or a congenital anomaly/birth defect.

Important medical events that may not result in death, are not immediately life-threatening, or require hospitalization may be considered serious when, based upon appropriate medical judgment, they may jeopardize the subject and may require medical or surgical intervention to prevent one of the outcomes listed in this definition. An example of such a medical event would be an allergic bronchospasm requiring intensive treatment in an emergency room or at home to prevent the development of one of the definitions above.

“Life-threatening” refers to an TEAE that at occurrence represents an immediate risk of death to a subject. An event that may cause death if it occurs in a more severe form is not considered life-threatening. Similarly, a hospital admission for an elective procedure is not considered an SAE.

All SAEs, as with any TEAE, will be assessed for severity and relationship to study intervention. All SAEs will be recorded on the appropriate AE e-CRF.

All SAEs will be followed through resolution or stabilization by a study clinician, licensed to make medical diagnoses and listed as the participating clinical site PI or appropriate sub-investigator.

All SAEs will be reviewed and evaluated by the Sponsor and will be reported to the IRB. This report will include severity, association with the study device, action(s) taken, and outcome.

9.2.6 Serious Adverse Event Reporting

Any TEAE that meets a protocol-defined criterion as an SAE must be submitted immediately (within 24 hours of site awareness) on an SAE form to CRO/EmitBio Inc. Pharmacovigilance:

EmitBio Pharmacovigilance

SAE Hot Line: [name] or [name]

Text Immediate Report: [name]

SAE Email: [contact]

In addition to the SAE form, all SAE data must be entered into the AE e-CRF.

Other supporting documentation of the event may be requested by EmitBio Pharmacovigilance and should be provided as soon as possible. The Sponsor Medical Monitor will review and assess the SAE for regulatory reporting and potential impact on study subject safety and protocol conduct.

At any time after completion of the study, if the participating clinical site PI or appropriate sub-investigator becomes aware of an SAE that is suspected to be related to study product, the participating clinical site PI or appropriate sub-investigator will report the event to the EmitBio Pharmacovigilance Group.

9.2.7 Regulatory Reporting of Device-related SAEs

Following notification from the participating clinical site PI or appropriate sub-investigator, EmitBio Inc., as the sponsor, will report to the FDA and will copy the clinical site investigators on all reports of potential serious risks from clinical studies of RD-X19, as soon as possible. EmitBio Inc. will report to the FDA any unexpected fatal or life-threatening suspected adverse reaction as soon as possible, but in no case later than 7 calendar days after the sponsor's initial receipt of the information. If the event is not fatal or life-threatening, an SAE safety report will be submitted within 15 calendar days after the sponsor determines that the information qualifies for reporting as specified in 21 CFR Part 312.32.

Relevant follow-up information to the safety report will be submitted as soon as the information is available. Upon request from FDA, EmitBio will submit to the FDA any additional data or information that the agency deems necessary, as soon as possible, but in no case later than 15 calendar days after receiving the request.

SAEs that are not considered related to RD-X19 will not be reported to the FDA.

